#### 6.1.2. Kits sent to / ordered by women

Sample tubes will be pre-labelled with a Preventx 'SK' number and barcode (standard barcode or two-dimensional barcode/Quick Response Code (QR code)). The Preventx 'SK' number and barcode will also be affixed to the Lab Request/Consent form and a unique ID number will be merged to print on the form. The unique ID number is generated by the coordinating centre and supplied to PSL. The unique ID number serves 2 purposes:

- allows the coordinating centre to identify whether the participant is from Group B or Group C).
- 2. Allows Group C participants to complete their self-sampling kit web or postal order Women will be instructed to write the date the sample was taken on the sample tube and Lab Request/Consent form (participants name, address and DOB prepopulated)

#### 6.2. Sample transport and storage

Samples will be transported dry and stored at room temperature.

#### 6.3. Residual samples

Residual samples will comprise of residual DNA stored in Roche transport media. After HPV results have been reported residual samples will be stored at room temperature by Preventx. Throughout the study, residual samples will be sent to the Molecular Epidemiology lab (MEL) at the Wolfson Institute of Preventive Medicine, Queen Mary University of London where they will be stored. Preventx will pseudonymise the samples and will retain a data linkage file (using the Preventx 'SK' number). The study team will then amalgamate this file with relevant data (age & histology from GP records) to provide to the QMUL laboratory for their analysis. In this way, the residual samples will be analysed anonymously by the MEL team, but the study team will be able to link the residual sample data to HPV result and final histology (if available).

At the end of the study residual samples will be stored in linked-anonymised format at the Molecular Epidemiology Laboratory at Queen Mary University of London, Wolfson Institute of Preventive Medicine, [name] under the institutional HTA storage license pending storage for possible future ethically approved analysis.

Potentially, residual samples will be made acellular before the end of the REC approval, in which case they would become not relevant material and will not require cover by the institutional HTA storage license. Results will not impact clinical management for women in the study.

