#### 2.3.3. Exploratory

- To pilot a variety of approaches to encourage GP practices to offer self-sampling opportunistically to women who are overdue cervical screening consult for any reason.
- To pilot a variety of approaches to facilitating women who wish to order a selfsampling kit.
- To compare demographic and cervical screening status (never screened, overdue, up-to-date) between responders and non-responders
- To examine the consultation rates and response rates (numbers offered, accepted, declined and returned as a proportion of total number of eligible women, reasons for declining kits, kit offers by health professional type) for eligible women in the opportunistic (intervention) arm.
- To assess the impact of offering self-sampling on cervical coverage using passive follow up data
- To carry out analysis on residual samples that could help inform management for cervical screening in the future

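### Section 6.3 provides for available histology to go to the laboratory analysing the residual samples, without masking or a rule that assay results come back first

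*Protocol*

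**What the plan says.** Protocol section 6.3 describes the path of the residual material once HPV results have been reported.

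- **Samples:** "Throughout the study, residual samples will be sent to the Molecular Epidemiology lab (MEL"), at Queen Mary University of London (QMUL).
- **Pseudonymisation:** "Preventx will pseudonymise the samples and will retain a data linkage file (using the Preventx 'SK' number").
- **Data to the laboratory:** the study team will then "amalgamate this file with relevant data (age & histology from GP records) to provide to the QMUL laboratory for their analysis".
- **Safeguard and linkage:** the next sentence presents this as the means by which "the residual samples will be analysed anonymously by the MEL team", and adds that "the study team will be able to link the residual sample data to HPV result and final histology (if available").
- **Effect on participants:** "Results will not impact clinical management for women in the study".

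The purpose is given in section 2.3.3, in the last of the exploratory objectives: "To carry out analysis on residual samples that could help inform management for cervical screening in the future". Appendix 1 repeats that objective without an endpoint or assessment method, and section 8.2 (Planned analysis) does not mention residual samples.

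**The concern.** Pseudonymised and masked are different properties. A pseudonym stops laboratory staff from knowing whose sample they hold. It does not stop them from knowing that the sample came from a woman with CIN2+ if a file keyed to the samples says so.

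Laboratory work on a new or exploratory assay usually involves judgement: where to place a cut-off, which failed or doubtful run to repeat, how to call a borderline signal. If those judgements are made with histology in hand and the results are then compared with the same histology, the apparent agreement can be too good. Section 2.3.3 intends the work to help shape future screening management, so an accuracy figure from it might be carried forward into later studies.

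**Working it through.** The protocol states no figure that depends on this point, so the check sets the provisions side by side.

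1. **Who analyses the samples?** Section 6.3: the Molecular Epidemiology laboratory at QMUL.
2. **Who is given histology?** Section 6.3: the QMUL laboratory, for its analysis. In this section that is the same laboratory.
3. **What protects the analysis?** Section 6.3 offers anonymity only. Sections 2.3.3, 6.3, 8.2, 9.2 and Appendix 1 contain no statement that assay readers are masked to disease status.
4. **Is an order fixed?** No. Samples travel throughout the study. Section 6.3 gives no date or condition for the file and does not make its release depend on the return of assay results.
5. **Does the laboratory need histology to run an assay?** Nothing in 6.3 says so. The study team can itself join residual-sample data to the HPV result and histology. Section 9.2 says that study data will be stored and analysed under the SK number or unique ID once identifiers are removed. A laboratory that returned results by SK number would give the study team what it needs for the linkage.
6. **For whom would histology exist?** Under section 5.9, HPV-positive women are advised to have cytology and are then managed on the cytology result. HPV-negative women are told that nothing further is needed, apart from those whose sample arrived after the 30-day validation period. Histology will therefore exist mainly for HPV-positive women who attended and were referred on. It follows that the mere presence of a histology entry tells the laboratory something about disease status, even before its content is read.

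Taken together, these steps show a data flow that permits assay decisions with the outcome known and a study team able to do the linkage without that exposure. They do not show that such decisions will be made that way.

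**The case against.** The best reply is that the protocol does not say when the file arrives. Providing it for the laboratory's analysis can mean data analysis after the assays are finished, and histology will often become available only well after the sample was sent. That is correct. A reader might infer that the laboratory would know which samples are CIN2+ while reading them. The text supports only that it could, because the order is left open.

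It can also be said that no accuracy study is specified. Section 6.3 names no assay, cut-off or reference standard, and the protocol mentions no sensitivity or specificity for the residual samples. This stands too: histology as the comparator is an inference from the planned linkage and the stated aim. Details of an exploratory assay may properly sit in a laboratory or analysis plan. What survives is that 6.3 is not merely silent. It specifies a transfer of histology to the analysing laboratory and relies on anonymity, which does not address masking.

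Three further inferences are tempting and not supported:

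- **Histology goes with every sample.** Section 6.3 limits it to where it is available, and most HPV-negative women would have none. For the same reason there is little basis for a claim about specificity, since no general verification of disease is planned in HPV-negative women.
- **The damage could not be undone.** Section 6.3 keeps the samples in linked-anonymised storage for possible later approved analysis, so masked retesting is possible in principle if enough material remains.
- **An automated assay would be equally exposed.** With preset cut-offs it would be less so; the protocol does not say which kind is meant.

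**Conclusion.** The point holds as a weakness in a stated step. Section 6.3 provides for available histology to reach the analysing laboratory, protects identity only, and does not require results first. If the assays are compared with histology, that can bias apparent accuracy. This rests on two assumptions that the protocol does not settle: that histology will serve as the comparator, and that the file may arrive before assay decisions are final.

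The reach is small. The objective is exploratory, in a pilot that section 8.2 describes as having no formal primary outcome measure. Uptake, follow-up attendance and turnaround times do not depend on it. The reported HPV results come from a different laboratory and are issued before the samples become residual. Section 6.3 rules out any effect on care.

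The size of any bias cannot be estimated from the protocol. A reader might try to attach one from the expected number of cases, as follows.

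- **Samples:** sections 8.1.1 and 8.1.2 give 210 + 1250 × 0.12 + 1250 × 0.07 = 447.5, taking 1250 women in each mailed group.
- **Cases:** if 8% to 15% are HPV positive and 10% to 30% of those have CIN2+ (assumed ranges, not in the protocol), there are 447.5 × 0.08 × 0.10 = 3.6 to 447.5 × 0.15 × 0.30 = 20.1 cases, or about 4 to 20.
- **With follow-up attendance:** at the 80% to 85% cited in section 5.9, the recorded cases would be about 3.6 × 0.80 = 2.9 to 20.1 × 0.85 = 17.1.

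With 4 to 20 cases, one changed call moves sensitivity by 1/20 = 5 to 1/4 = 25 percentage points. That is only the coarseness of a small sample and applies equally to a masked error. It says nothing about how often knowledge of histology would change a call, and should not be read as the bias.

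**What to change.** Amend section 6.3 so that the QMUL laboratory receives and analyses the residual samples under pseudonymised SK numbers only. State that histology, and age unless the assay itself needs it, will be released to the laboratory, or linked by the study team, only after assay results and any cut-offs have been locked and returned. If some assays have already been run, record whether histology was with the laboratory at the time and say so when reporting.

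The cost is about one sentence in 6.3 and a later date for sending one file. No additional samples, staff or procedures are required, and the linkage that section 6.3 already foresees is kept.

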#### 7. LABORATORY

HPV testing for the study will be performed by Preventx, [name].

#### 7.1. HPV testing

Preventx will use Roche cobas® 6800 platform for HPV testing. The cobas® 6800 Human Papillomavirus (HPV) Test is a qualitative in vitro test for the detection of Human Papillomavirus in patient specimens. The test utilises amplification of target DNA by the Polymerase Chain Reaction (PCR) and nucleic acid hybridisation for the detection of 14 highrisk (HR) HPV types in a single analysis. The test specifically identifies (types) HPV16 and HPV18 while concurrently detecting the rest of the high-risk types (31, 33, 35, 39, 45, 51, 52, 56, 58, 59, 66 and 68) at clinically relevant infection

HPV testing will be performed using the Roche's CE marked HPV test kits. Samples will be prepared into PCR Media, following the Roche guidelines and to the applicable standards outlined in the laboratory quality manual. Testing will be carried out in the Preventx Laboratory (Preventx, [name]).

The laboratory will aim to process samples and send out results within 5 working days of receipt. Results will be reported via Preventx's integrated testing platform and will be accessible via Preventx's secure online reporting tools.

#### 7.2. Reporting of HPV test results

Preventx will send HPV test results to the study team via a secure results reporting platform. The team will then personalise a pre-determined 'HPV result' letter and send to the study participant in the post. The HPV positive result letter will be accompanied with the study specific HPV Information Sheet for their reference. HPV results will be sent to the participant's GP on a weekly basis via NHS.net accounts and hard copies will follow in batches on a monthly basis by post. Study HPV test results will be entered on the GP medical record system as Read codes by the practice administrative staff.

#### 8. STATISTICAL CONSIDERATIONS

#### 8.1. Sample size considerations

With 13 participating GP practices there would be approximately 8420 eligible women (i.e. women aged 25-64 eligible for cervical screening who are overdue by at least 6 months).

#### 8.1.1. Intervention arm – Opportunistic offering of self-sampling

With six GP practices randomised to the intervention arm, there would be some 4000 eligible women. Based on a previous study[19]) we estimate that 60% will consult their GP practice over one year, 500 (21%) will be opportunistically offered a self-sampling kit and  $\sim$ 330 (14%) will accept (4000\*0.60\*0.14). An estimated 210 (9%) (4000\*0.6\*0.09) would return a self-sample for HPV testing. Therefore, the proportion of women >6m overdue cervical screening who will return a sample when opportunistically offered a kit (i.e.  $\approx$ 210/2400) could be estimated with a 95% confidence interval of width  $\pm$ 1.0%.

#### 8.1.2. Individual level randomisation

With 13 GP practices we anticipate that some 5000 will be identified as never screened or will reach the 15- or 27-month anniversary of their last test due date during the study. Of these, approximately 2500 women will be randomised to each of the two intervention arms. If we assume that 12% of those who are sent a kit (initially) return an adequate sample, the expected 95% confidence interval would be estimated with approximately ±1%. If about 7% of those offered a kit request one and return an adequate sample, then this could be estimated with approximately ±1%. Therefore, for 13 GP practices approximately 1250 invitation letters will be sent (here, the number of self-sampling kits will depend on the women's willingness to participate) and 1250 self-sampling kits posted.

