#### **STUDY SYNOPSIS**

Chart Title	A Landan LIDV Call Compline Dilat			
Short Title	A London HPV Self Sampling Pilot			
	A pragmatic, factorial cluster randomised controlled pilot study (a 2 x3 factorial design, with the 3-way (individual level) randomisation nested within the 2-way (GP-level) randomisation.			
Methodology	GP practices will be randomised 1:1 to either offering self- sampling kits (SSK) opportunistically to women overdue (>6 months) cervical screening when they present for any reason (intervention arm) or usual care (control arm).			
	The second (nested) randomisation will be individual level randomisation of women within each GP practice who have never been screened or who reach the 15- or 27-month anniversary of the date their last cytology test was due without being screened (by self-sample or cytology). 2:1:1 to either: Group A Usual care (control). Group B Receiving a letter inviting them to order a kit, or Group C: Receiving a kit in the post.			
Research Sites	~13 GP practices in London			
Aim	To assess feasibility and optimal approaches for offering self-sampling to cervical screening non-attenders in London to increase coverage.			
Objectives	A summary table of study objectives, endpoints and method of assessment is located in Appendix 1 .			
	For GP-level randomisation:  ~8420 women in total will be eligible (i.e. >6m overdue cervical screening) within 13 GP practices of which we estimate the following:  • ~500 will be offered SSKs opportunistically (330 will accept and ~210 will return a self-sample)			
Number of participants	For individual-level randomisation:  • ~5000 (i.e. never screened or 15- or 27-month anniversary of the date their last cytology test) will be individually randomised  • ~2500 will receive an SSK or letter inviting them to order an SSK via individual level randomisation of which 175-300 will return a self-sample			
Inclusion criteria	
 
GP-level randomisation
 
Women aged 25-64 years who are eligible for cervical screening and are least 6 months overdue (i.e. no cervical cytology recorded in the GP records in the past 3.5 years if aged 25-49 or 5.5 years if aged 50-64)
 
			

·	
	Individual-level randomisation
	Never-screened women & women who reach the     15 months* of last smear due date (and not screened by smear or self-sample)      Women unable to provide informed consent (e.g.
	because of learning difficulties)

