#### 4. STUDY DESIGN

A randomised controlled pilot in GP primary care using a 2x3 factorial design, with the 3-way (individual-level) randomisation nested within the 2-way (GP-level) randomisation (see Figure 1 Study Schematic).

Approximately 13 GP practices in Hounslow CCG (Clinical Commissioning Group) will be included initially. Additional GP practices and CCGs may be added as the study progresses.

The first randomisation will be GP practices in the ratio 1:1 to either:

- Intervention arm Offering self-sampling kits opportunistically to women overdue cervical screening by at least 6 months when they present to GP primary care for any reason, and
- 2. Usual care (control) women will receive the usual smear reminder letter.

Practices will be randomised in a single block of 12 (with 6 in each arm) using computergenerated random numbers. We may stratify by list size if there are large differences between participating practices.

The second (nested) randomisation will be individual level randomisation of women within each GP practice who have never been screened or who reach the 15-month anniversary of the date their last cytology test was due without being screened (by self-sample or cytology). Women who are already past the 15-month anniversary of their last test due date at study start will be randomised if they reach the 27-month anniversary (i.e. women who are between 16 and 27 months past their last test due date). This will allow all women who are overdue screening by at least 15 months to be randomised while avoiding inviting women to self-sampling too close to their next invitation (women aged 25-49 are invited every 36 months). Randomisation at the 27 month anniversary of last test due date will only take place for the first 12 months of the study. This will avoid women being randomised more than once. Never screened women will be randomised in batches throughout the study (e.g. according to birth month or by counting 15m from their last test due date if they had attended when invited), rather than all at a single time point.

Individual-level randomisation of women will be in the ratio of 2:1:1 to either:

[figure not shown]
- Group A: Usual care (control).
- Group B: Receiving a letter inviting them to order an SSK
- Group C: Receiving an SSK in the post.

The planned pilot trial duration is up to 12 months for the active recruitment phase.

Figure 1 Study Schematic

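### Section 8.1.2 puts 2500 women in each mailed arm, but 5000 women at 2:1:1 gives 1250, where precision is about ±1.8 and ±1.4 points rather than ±1%

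*Protocol*

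**What the plan says.** The total is given in Protocol Section 8.1.2: "With 13 GP practices we anticipate that some 5000 will be identified as never screened" or will reach the 15- or 27-month anniversary. The next sentence reads "Of these, approximately 2500 women will be randomised to each of the two intervention arms".

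The paragraph then gives precision. For women sent a kit, with 12% assumed to return an adequate sample, "the expected 95% confidence interval would be estimated with approximately ±1" per cent. For women invited to order, with 7% assumed, the same figure of about ±1% is given.

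The last sentence of the paragraph uses a different arm size: "approximately 1250 invitation letters will be sent" "and 1250 self-sampling kits posted".

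Section 4 fixes the allocation: "Individual-level randomisation of women will be in the ratio of 2:1:1 to either" usual care (Group A), a letter (Group B) or a posted kit (Group C). Section 5.3 and the Study Synopsis repeat the ratio. The Synopsis counts Groups B and C together: about "2500 will receive an SSK or letter inviting them to order an SSK via individual level randomisation", "of which 175-300 will return a self-sample".

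**The concern.** Two arms of 2500 would use up all 5000 women and leave nobody for usual care, which under 2:1:1 should hold half of them. The sentence therefore conflicts with the allocation ratio, with the Synopsis and with the end of its own paragraph.

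The conflict matters because the ±1% figures sit in the same paragraph and fit the doubled arm size. Section 2.3.1 makes estimation of uptake the primary objective, under three approaches, and Section 8.1.2 covers two of them. The protocol offers interval width, not power, to show what its numbers can deliver. A reader judging whether these two estimates will be precise enough is given figures that the design does not produce. Someone later comparing the achieved arm sizes with the stated 2500 would also see a halving that is not real.

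**Working it through.** **Inputs**
- Total individually randomised: about 5000 (Section 8.1.2).
- Allocation A:B:C of 2:1:1 (Sections 4 and 5.3, Synopsis).
- Assumed uptake: 12% for posted kits (C), 7% for invitations to order (B) (Section 8.1.2).
- Confidence level 95%; stated half-width about ±1% for both (Section 8.1.2).

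**Step 1: arm sizes from the ratio**
- A: 5000 × 2/4 = 2500
- B: 5000 × 1/4 = 1250
- C: 5000 × 1/4 = 1250
- B and C together: 2500, as in the Synopsis.

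**Step 2: the plan's own figure, at its stated 2500 per arm**

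Half-width = 1.96 × √(p(1 − p)/n).
- 12%: 1.96 × √(0.12 × 0.88/2500) = 1.27 points
- 7%: 1.96 × √(0.07 × 0.93/2500) = 1.00 points

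To the nearest whole per cent, both are ±1%. The stated precision is reproduced at 2500 per arm.

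**Step 3: the same formula at 1250 per arm**
- 12%: 1.96 × √(0.12 × 0.88/1250) = 1.80 points
- 7%: 1.96 × √(0.07 × 0.93/1250) = 1.41 points

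Halving n widens each interval by √2, about 1.41.

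**Step 4: does the interval method matter?**

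| Half-width at n = 1250 (points) | 12% | 7% |
|---|---|---|
| Normal approximation, 95% | 1.80 | 1.41 |
| Wilson, 95% | 1.80 | 1.42 |
| Clopper-Pearson, 95% | 1.84 | 1.46 |
| Normal approximation, 90% | 1.51 | 1.19 |

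The choice of 95% method makes almost no difference. At 12%, even a 90% interval is wider than ±1.5 points.

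**Step 5: numbers needed for exactly ±1.0 point**

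n = 1.96² × p(1 − p)/0.01², giving about 4057 women at 12% and about 2501 at 7%.

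**Step 6: cross-check against the Synopsis returns**
- 7% of 2500 = 175 and 12% of 2500 = 300, which are the ends of the Synopsis range.
- At 1250 per arm: 1250 × 0.12 + 1250 × 0.07 = 150 + 87.5 = 237.5, inside the range.
- At 2500 per arm: 300 + 175 = 475, outside it.

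The Synopsis therefore also treats 2500 as the total for the two arms.

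**The case against.** The best defence is that this is a drafting slip with little practical effect. The correct arm size can be recovered from the same paragraph and from the Synopsis, and the allocation ratio and mailing volumes are right. Section 5.3 randomises all eligible women in the participating practices, so the number was not chosen to reach ±1%. Section 8.2 states that there is no formal primary outcome measure, and no power claim depends on the figure. Reported intervals will use the numbers actually randomised. Recruitment was due to end in March 2020, before the current version of October 2021. All of this stands and lowers the severity. It does not make the sentence or the precision figures correct.

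A second defence is the word *approximately*. At whole-per-cent rounding, ±1.41 is still ±1%, so the letter arm is only mildly misdescribed. That is fair for the letter arm, but ±1.80 rounds to ±2%, so it does not cover the posted-kit arm.

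A reader might also infer stronger points that the protocol does not support:
- *That ±1% is wrong at 12% even with 2500 per arm.* The half-width there is 1.27 points, which fits an approximate whole-per-cent figure.
- *That the Synopsis range of returns is wrong.* It is 7% to 12% of the correct combined total and contains the expected figure of about 238.
- *That ±1% was demonstrably calculated from 2500.* The figures match that arm size, but Section 8.1.2 shows no calculation, so this remains an inference.
- *That the pilot is under-recruited or must enlarge.* Nothing in the protocol makes ±1% a requirement.

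**Conclusion.** The point holds as an error of wording and arithmetic in Section 8.1.2. About 2500 women are allocated to the two intervention arms combined, 1250 to each. At that size the 95% half-widths are about ±1.8 points for posted kits and ±1.4 points for invitations to order, against a stated figure of about ±1% for both. The discrepancy is clear in the first arm and modest in the second.

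This rests on the protocol's own total, ratio and uptake assumptions, and on a simple binomial interval with independent responses. It should be corrected because it misdescribes two of the three primary-objective estimates. It is not a serious fault in an estimation pilot whose allocation and mailing numbers are already right.

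**What to change.** In Section 8.1.2, change the number randomised to each intervention arm from 2500 to about 1250. In the same paragraph, restate the expected 95% precision as about ±1.8% for women sent a kit (12% uptake) and about ±1.4% for women invited to order (7% uptake). Both changes are needed: correcting the arm size alone would leave precision figures that do not match it.

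The last sentence of the section, the allocation ratio and the Synopsis, including its range of returns, can stay as they are. Correcting the error needs no change to enrolment. The cost is a few words and a less favourable precision statement.
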